6.2.2.2. Analysis of time from randomization to a Kidney Clinical Event

A stratified log-rank test stratified by randomization stratification factors will be used to evaluate SEL treatment effect on time from randomization to a Kidney Clinical Event. Hazard ratio (HR) and 95% CI comparing the SEL and placebo arms will be estimated using a stratified Cox proportional hazard model, stratified by randomization stratification factors. Number and percent of subjects with event per treatment group, event rate, HR, 95% CI and p-value will be presented for analysis of time to the first Kidney Clinical Event, and time to each component of the Kidney Clinical Event endpoint. HR and 95% CI will only be reported for outcomes with more than 10 events, and have at least 1 event in each treatment arm. Event rate will be calculated as the number of subjects with the event, divided by the total duration of follow-up across all subjects in a given treatment group. Follow-up time for each subject will be calculated as time from Randomization to the earliest of study completion, premature study discontinuation, death and event of interest for a given outcome.

Sensitivity analyses will be performed based on different definition of events or population.

The same approaches as described in Sections 6.2.2.1 and 6.2.2.2 will be used for hypothesis testing for Kidney Clinical Events for the following:

- Sensitivity analysis where in the SEL group, a 40% reduction in $eGFR_{cr}$ will be calculated from the pre-run-in Baseline $eGFR_{cr}$ for off-treatment $eGFR_{cr}$ values and the post-run-in Baseline $eGFR_{cr}$ for on-treatment $eGFR_{cr}$ values.
- Sensitivity analysis to use treatment-specific Baselines to calculate $eGFR_{cr}$ percent decline. For all $eGFR_{cr}$ values in the SEL group, a 40% reduction in $eGFR_{cr}$ will be calculated using the post-run-in Baseline $eGFR_{cr}$.
- Sensitivity analysis to evaluate the impact of attenuation of the acute effect. For subjects in the SEL group, the on-treatment $eGFR_{cr}$ values will be adjusted using a regression model as described in [Appendix 2](#), which takes into account attenuation of the acute treatment effect that may be due to the theoretical concern for loss of kidney function over time. This adjusted on-treatment $eGFR_{cr}$ value will be compared with the pre-run-in Baseline $eGFR_{cr}$ to calculate an adjusted percent $eGFR_{cr}$ reduction. For subjects in the placebo group, percent $eGFR_{cr}$ reduction will be calculated by comparing observed $eGFR_{cr}$ values with the pre-run-in Baseline $eGFR_{cr}$.
- Sensitivity analysis in subjects who completed study treatment.
- Sensitivity analysis excluding subjects with randomization stratification mismatch between IXRS and Clinical Database.
- Sensitivity analysis excluding subjects who took prohibited medications that may affect SEL efficacy or decrease SEL drug level in the prohibited period as detailed in [Appendix 3](#).

- Sensitivity analysis where a 57% reduction in $eGFR_{cr}$ from pre-run-in Baseline will be used for the $eGFR_{cr}$ reduction component of the Kidney Clinical Events instead of 40% reduction.
- Sensitivity analysis for the Kidney Clinical Events based on $eGFR_{cys}$. The Kidney Clinical Events endpoint will have the same definition as in Section 6.2.1, except that the $eGFR$ reduction and $eGFR < 15$ components will be based on $eGFR_{cys}$ instead of $eGFR_{cr}$.

The same approaches as described in Sections 6.2.2.1 only will be used for hypothesis testing for Kidney Clinical Events for the following:

- The proportion of Kidney Clinical Events by Week 48 will be compared between SEL and placebo treatment arms. Subjects who do not have sufficient measurements to determine whether or not they had a Kidney Clinical Event by Week 48 will be considered not having a Kidney Clinical Event by Week 48.

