6.7.3. Remote Assessments

Subjects who have permanently discontinued study drug, reached kidney failure, or are no longer able to continue to attend clinic visits in-person, and **have not withdrawn full consent** will be asked to continue study participation through remote contact, without in-clinic study visits. Subjects will be contacted approximately every 24 weeks until the global study end date. At a minimum, subjects will be contacted at the global study end date.

Subjects will be contacted via telephone, email, or other contact methods through friends or family. Details regarding discussions via telephone, email, or other contact must be properly documented by the site in the source records, including the responses from the subject. The investigator will make every effort to contact the subject or a close relative or caretaker by phone to collect information. The investigator should show due diligence by documenting in the source documents steps taken to contact the subject (e.g., dates of phone calls, registered letters, etc.).

Follow-up for survival, kidney outcomes, and safety will continue until reasons listed in protocol Section 3.5 are met or until the global study end date.

Information gathered will include:

- Survival status
- Death details, if applicable
- Receipt of kidney transplant
- Dialysis initiation post study drug discontinuation
- AE and SAE collection per protocol Section 7

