6.2. Secondary Endpoints

6.2.1. Definition of Secondary Endpoints

Secondary endpoints for this study are:

- Proportion of Kidney Clinical Events defined as any of the following events:
 - Confirmed $\geq 40\%$ decline in eGFR_{cr} from pre-run-in Baseline, or
 - Kidney failure (dialysis performed for at least 4 weeks, kidney transplantation, or confirmed decrease in eGFR_{cr} to < 15 mL/min/1.73 m² for subjects without dialysis or kidney transplantation), or
 - Death due to kidney disease

The $\geq 40\%$ decline in $eGFR_{cr}$ from Baseline and sustained decrease in $eGFR_{cr}$ to <15 mL/min/1.73 m² components need to be confirmed at the next scheduled visit but at least 4 weeks after the index measurement (i.e., the first measurement of $\geq 40\%$ decline in $eGFR_{cr}$ from Baseline or $eGFR_{cr} < 15$ mL/min/1.73 m²). Events of $eGFR_{cr}$ decline $\geq 40\%$ from Baseline or $eGFR_{cr} < 15$ mL/min/1.73 m² without confirmation due to study discontinuation (e.g., death or lost to follow-up) will be included in the analysis and counted as events. Date of the index measurement will be used as the date of event in the analysis.

- Time from randomization to first occurrence of a Kidney Clinical Event

If a subject has not experienced any Kidney Clinical Events at the time of global study end date/early discontinuation of the study, this subject will be censored at the time of the last assessment of kidney function.

- $eGFR_{cys}$ slope from pre-run-in Baseline through Week 84

The values for $eGFR_{cys}$ will be calculated using the CKD-EPI Cystatin C Equation (2012):

$$eGFR = 133 \times \min\left(\frac{S_{cys}}{0.8}, 1\right)^{-0.499} \times \max\left(\frac{S_{cys}}{0.8}, 1\right)^{-1.328} \times 0.996^{Age} \times 0.932[if\ female]$$

S_{cys} = standardized serum cystatin C (mg/L)

min indicates the minimum of $S_{cys}/0.8$ or 1

max indicates the maximum of $S_{cys}/0.8$ or 1

age in years

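### The Kidney Clinical Event rate counts follow-up time without eGFR that the log-rank and Cox analyses censor, so composite and eGFR-based rates are biased low or at best equal

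*SAP*

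**What the plan says.** SAP 6.2.2.2 defines the rate: "Event rate will be calculated as the number of subjects with the event, divided by the total duration of follow-up across all subjects", separately for each arm. The clock follows: "Follow-up time for each subject will be calculated as time from Randomization to the earliest of study completion". Three other dates can end it sooner, namely early exit from the study, death, and the event being analysed. The rate is reported alongside the model results: "event rate, HR, 95% CI and p-value will be presented for analysis of time to the first Kidney Clinical Event, and time to each component".

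The survival analyses use another end point. SAP 6.2.1 says of a subject without a Kidney Clinical Event that "this subject will be censored at the time of the last assessment of kidney function". Protocol 8.5.2.2 gives the same rule. Neither document defines an assessment of kidney function, and the SAP gives no separate censoring rule for the components.

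The documents also describe study time in which no eGFR is drawn:

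- **Remote follow-up (Protocol 6.7.3).** Certain subjects "will be asked to continue study participation through remote contact, without in-clinic study visits". The items collected include survival, death details, transplant and "Dialysis initiation post study drug discontinuation". eGFR is not among them, and Protocol 6.4.12 accepts only central-laboratory eGFR for efficacy.
- **After kidney failure (Protocol 6.5).** Subjects move to remote follow-up once the 30 Day EOT Follow-up visit is done.
- **30 Day EOS Safety Follow-up (Protocol Appendix 2).** No eGFR is marked, and the contact may be by telephone.

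No section reconciles the two clocks or says that the difference is intended.

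**The concern.** In a person-time rate, the denominator should cover the time in which a numerator event could be recorded. A 40% decline or an eGFR below 15 cannot be recorded when no central sample is taken. The survival analyses respect this by stopping at the last kidney-function assessment; the rate does not. One table would then carry two definitions of time at risk without saying so.

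What is at stake is descriptive. Readers use event rates to judge absolute risk, to compare with other trials and to plan the next one. Rates diluted by unobservable time understate that risk.

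**Working it through.** **The plan's own figure.** The documents state no Kidney Clinical Event rate, event count or hazard ratio, so there is nothing to reproduce for this endpoint. The one design figure is power for the primary slope comparison (SAP 1.3: 99% and 97%). It recomputes to 98.5% and 97.2%, and this point does not depend on it.

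**Direction.** A subject with the event contributes the same time under both rules. An event-free subject contributes time to study exit under the rate rule and time to the last kidney assessment under the censoring rule. The last assessment cannot fall after exit. So the rate denominator is never smaller, and it is larger once any event-free subject has a gap. With the same numerator:

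SAP rate / censoring-consistent rate = (F − g) / F

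where F is mean follow-up to study exit and g is the mean gap from last kidney assessment to exit. The ratio cannot exceed 1.

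**Size.** Neither F nor g is in the documents, so these are scenarios:

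- F = 48, 84 and 120 weeks. 84 weeks is the horizon of the primary slope in the SAP, not a stated mean follow-up.
- A gap of 30 days (30/7 = 4.29 weeks), if study exit is dated at the EOS safety contact.
- Gaps of 12 to 36 weeks in 15% of subjects (the dropout figure in SAP 1.3) or 23% (22.8% stopped drug in the earlier Phase 2 study, Protocol 1.2.3.2.2). Both shares are borrowed. Neither document says how many subjects will go remote.

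| Scenario | g (weeks) | F = 48 | F = 84 | F = 120 |
|---|---|---|---|---|
| Last eGFR on exit date | 0 | 1.000 | 1.000 | 1.000 |
| 30 days in all | 4.29 | 0.911 | 0.949 | 0.964 |
| 12 weeks in 15%, none in the rest | 1.80 | 0.963 | 0.979 | 0.985 |
| 12 weeks in 15%, 30 days in the rest | 5.44 | 0.887 | 0.935 | 0.955 |
| 24 weeks in 15%, 30 days in the rest | 7.24 | 0.849 | 0.914 | 0.940 |
| 36 weeks in 15%, 30 days in the rest | 9.04 | 0.812 | 0.892 | 0.925 |
| 36 weeks in 23%, 30 days in the rest | 11.58 | 0.759 | 0.862 | 0.903 |

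Example: 0.85 × 4.29 + 0.15 × 36 = 9.04, and (84 − 9.04)/84 = 0.892. The table gives every subject a gap. Subjects with the event have none, so it slightly overstates the effect.

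**Simulation with events included.** Assume a true composite hazard of 0.10 per year, 84 weeks, 15% going remote at a random time, a 30-day gap in the rest, and dialysis, transplant and kidney death still detected after the last eGFR.

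| Outcome | True | Current rule | Denominator ending at last eGFR |
|---|---|---|---|
| Composite, all events eGFR-driven | 0.100 | 0.088 | 0.100 |
| Composite, 80% eGFR-driven | 0.100 | 0.091 | 0.102 |
| Dialysis, transplant or kidney death alone | 0.020 | 0.020 | 0.0225 |

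The last row matters: for events that remote contact does capture, the longer clock is the right one.

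**The 40%-decline component.** Its clock stops only at its own event. A subject with a pre-run-in baseline of 20 who falls just below 15 has declined about (20 − 15)/20 = 25%. That subject reaches kidney failure, moves to remote follow-up and keeps adding person-time to the 40% component after eGFR collection ends. This can happen at any baseline below 25, since 0.6 × 25 = 15. The gap is built into the protocol and does not depend on subject preference.

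**The case against.** The strongest reply is that little time may be affected. The rate clock also stops at premature study discontinuation, death or the event, so only event-free subjects can add excess time. After stopping drug, the default is the full visit schedule (Protocol 6.7.1). Limited follow-up still draws eGFR every 12 weeks (6.7.2), and the EOT and 30 Day EOT visits both include eGFR. Remote contact is the last resort. The EOS visit also has eGFR marked, so the 30-day gap vanishes if study completion is dated there. If a remote contact about dialysis or transplant counts as an assessment of kidney function, the clocks come closer still. All of this stands. It limits the size but does not remove the mismatch.

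A reader might infer that the bias favours SEL, because drug discontinuation in the earlier Phase 2 study was 28.9% at 18 mg and 22.4% on placebo. With 25 to 50% of stoppers going remote and stops spread evenly, the lost share is stop rate × remote share × 0.5: 3.6 to 7.2% on SEL and 2.8 to 5.6% on placebo. The rate ratio would then shift by about 0.8 to 1.7% towards SEL. The documents do not support this:

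- The remote share has no source.
- The Phase 2 stops include progression to ESKD (13 of 57 pooled SEL, 4 of 19 placebo), which here would be events, and withdrawal of consent (13 and 3), which may end study participation. Applying the pooled SEL mix to 18 mg, removing ESKD leaves about 0.6 to 1.2%. Removing consent withdrawals too leaves 0.2 to 0.4%.
- The difference, 24/83 against 19/85, is 6.6 points with an approximate 95% interval of −7 to +20. The 2 mg and 6 mg groups stopped less often than placebo.
- Protocol 4.4 randomizes only subjects who did not permanently stop drug in a run-in that includes at least 4 weeks of SEL 18 mg, which should remove some early stoppers.

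A reader might also expect the rates to disagree visibly with the hazard ratio. A crude rate ratio need not equal a stratified Cox hazard ratio, so disagreement would not itself show an error.

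**Conclusion.** The mismatch is in the text and its direction follows from arithmetic: rates for the composite and its eGFR-based components will be at or below the rate consistent with the survival analysis. The size is unknown. It is zero if the last eGFR falls on the exit date, and about 2 to 14% at a mean follow-up of 84 weeks under the assumed gaps. Across 48 to 120 weeks the scenarios run from no effect to about 24%. Rates for dialysis, transplant or kidney death as separate components need not be low.

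The log-rank test, hazard ratio, confidence interval and p-value do not use this denominator and are unaffected. The ratio of rates between arms is distorted only if the gap differs by arm, and the documents establish no direction for that. This is a minor point about descriptive rates.

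**What to change.** In SAP 6.2.2.2:

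1. For the composite and the eGFR-based components, including kidney failure where it contains the eGFR below 15 criterion, take person-time as each subject's time-to-event analysis time (event or censoring date). Count the same events in the rate as in the Cox model.
2. For dialysis, transplant and kidney death analysed as separate components, keep follow-up to study exit or last remote contact.
3. Define an assessment of kidney function, and say whether a remote dialysis or transplant contact counts, so that numerator and denominator match for each outcome.

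The cost is a few sentences in the SAP and no new data. There is one small downside. In the composite, remotely captured dialysis, transplant or kidney death stays in the numerator while event-free remote time leaves the denominator, so the rate may be slightly high: about 0.102 against a true 0.100 in the simulation, compared with 0.091 under the current rule.

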5.4. Prior and Concomitant Medications

All concomitant medications will be recorded in the source documents and eCRFs. This includes concomitant medications taken within 30 days prior to Screening; concomitant medications of interest, as defined in Section 6.4.2, up to 1 year prior to Screening; and any taken during the study through the 30 Day EOS Safety Follow-up visit or until subjects are being followed via remote assessments as defined in Section 6.7.3.

The following medications are prohibited:

- Any investigational medication or device within 30 days or within 5 half-lives of the prior investigational agent (whichever is longer) prior to Enrollment and throughout the study
- Concurrent use of study drug with both an ACEi and ARB
- Strong cytochrome P4503A4 (CYP3A4) inducers may decrease the exposure of SEL and could lead to decreased efficacy. Use of strong CYP3A4 inducers is prohibited from 2 weeks prior to Enrollment through end of treatment
- Inhibitors of kidney transporter-mediated creatinine secretion may impact the assessment of efficacy. Use of inhibitors of creatinine secretion is prohibited from 2 weeks prior to Enrollment through end of study

Caution should be exercised when co-administering sensitive P-gp substrates with narrow therapeutic index with SEL as it may increase the concentrations of these agents. Investigators should refer to the full prescribing information for additional guidance on use of concomitant medication with a P-gp inhibitor.

Examples of representative medications that are prohibited 2 weeks prior to enrollment or which should be used with caution starting at enrollment are listed in [Table 5-1](#). This is not an exhaustive list of medications that are prohibited or to be used with caution. If there are questions about concomitant medications, please contact the Gilead Medical Monitor or Sponsor Designee.

Table 5-1. Examples of Medications that are Prohibited or to be Used with Caution^a

Drug Class	Agents Prohibited
	Prohibited 2 weeks prior to enrollment through the end of study
Antianginals ^b	ranolazine ^c
Antiarrhythmics ^b	amiodarone ^d , dronedarone ^c , dofetilide ^c
Antibiotics ^b	trimethoprim
Antifungals ^b	isavuconazole ^c
Antiparasitics ^b	pyrimethamine ^c
Direct renin inhibitors (DRI) ^c	aliskiren ^f
H2 Blockers ^{b,i}	cimetidine, famotidine
Mineralocorticoid receptor antagonists (MRA) ^c	spironolactone, eplerenone
Nuclear factor erythroid 2-related factor 2 (Nrf2) activator	bardoxolone ^c

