Drug Class	Agents Prohibited
	Prohibited 2 weeks prior to enrollment through the end of treatment
Anticonvulsants ^g	phenobarbital, phenytoin
Antimycobacterials ^g	rifampin
Herbal/Natural Supplements ^g	St. John's Wort

Category	Agents to be used with caution
	Use with caution from enrollment through end of treatment
Cardiac Medications ^f	digoxin ^h , dabigatran etexilate, flecainide
Antineoplastic/immunosuppressant ^f	methotrexate

- a Not all of these example medications may be approved in each of the countries where the study is being conducted; please refer to local product information
- b May increase serum creatinine and decrease eGFR.
- c Not approved in Japan
- d Due to the long half-life of amiodarone, prohibited 90 days prior to enrollment through end of the study
- e Disallowed if concurrent use with ACEi or ARB for at least 2 weeks prior to Enrollment. If subject cannot tolerate ACEi or ARB, subject may use either a DRI OR an MRA as a single agent. If medically necessary after Week 12, concurrent use of MRA with ACEi or ARB is permitted. However, concurrent use with ACEi or ARB is associated with risk of hyperkalemia, so caution must be exercised. Please refer to full prescribing information for additional guidance.
- f SEL may increase the exposure of these medications and must be used with caution. Please refer to the full prescribing information for additional guidance
- g May result in a decrease in the concentration of SEL
- h Digoxin level should be measured at Visit C and Week 4. PI may continue checking after Week 4 as part of digoxin management as needed. Monitor and adjust digoxin dose as necessary based on prescribing information
- i Permissible H2 blockers include ranitidine, nizatidine, roxatidine, and lafutidine.

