- Sensitivity analysis of eGFR_{cr} slope excluding off-treatment eGFR_{cr} values from the SEL treatment group.

- Sensitivity analysis of eGFR_{cr} slope excluding eGFR_{cr} values collected after the initiation of dialysis or kidney transplantation.
- Sensitivity analysis to evaluate the impact of attenuation of the acute effect. For subjects in the SEL group, the on-treatment eGFR_{cr} values will be adjusted using a regression model as described in [Appendix 2](#), which takes into account attenuation of the acute treatment effect that may be due to the theoretical concern for loss of kidney function over time. For subjects in the placebo group, the observed eGFR_{cr} values will be used. The analysis of eGFR_{cr} slope will be performed using the same model as described in the primary analysis, except that pre-run-in Baseline eGFR_{cr} will be used for both SEL and placebo arms.
- Sensitivity analysis of eGFR_{cr} slope in subjects who completed study treatment.
- Sensitivity analysis of eGFR_{cr} slope excluding subjects with randomization stratification mismatch between IXRS and Clinical Database.
- Sensitivity analysis of eGFR_{cr} slope excluding subjects who took prohibited medications that may affect SEL efficacy or decrease SEL drug level in the prohibited period as detailed in [Appendix 3](#).
- Sensitivity analysis of eGFR_{cr} slope from pre-run-in Baseline for both SEL and placebo arms.
- Sensitivity analysis of eGFR_{cr} slope from treatment-specific Baselines through Week 48.
- Sensitivity analysis of eGFR_{cr} slope from treatment-specific Baselines through Week 60.
- Sensitivity analysis of eGFR_{cr} slope from treatment-specific Baselines through Week 72.
- Sensitivity analysis of eGFR_{cr} slope from treatment-specific Baselines through Week 96.

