Appendix 2. Adjustment of On-Treatment eGFR_{cr} Values

For subjects in the SEL treatment group, the on-treatment eGFR_{cr} values will be adjusted using a regression model. The statistical methods are described below. For subjects in the SEL treatment group whose off-treatment eGFR_{cr} data are not collected, or who experience a decrease in eGFR of $\geq 40\%$ relative to Baseline as a primary clinical endpoint event before treatment discontinuation, their eGFR values after treatment discontinuation will be imputed using a regression model. The statistical methods are described below.

The following linear regression model will be fitted for subjects in the SEL treatment group whose off-treatment eGFR_{cr} values are collected in the study:

$$\delta = \alpha + \beta x + \epsilon$$

Where δ is the change in eGFR_{cr} values after treatment discontinuation defined as the first observed eGFR_{cr} value at least 7 days after treatment discontinuation minus the last observed eGFR_{cr} value before treatment discontinuation; x is the last observed eGFR_{cr} value before treatment discontinuation, α is the intercept, β is the coefficient for x , and ϵ is the residual.

This model will then be used to predict the unobserved eGFR_{cr} change after treatment discontinuation for subjects in the SEL treatment group. Specifically, the x term in the model is the observed eGFR_{cr} value at each visit, and the outcome δ is the predicted eGFR_{cr} change if subject hypothetically discontinues SEL treatment at each visit.

On-treatment eGFR_{cr} values will then be as adjusted by adding δ to the observed eGFR_{cr} values. These adjusted eGFR_{cr} values will be used in the sensitivity analyses for primary and some secondary endpoints, as described in Sections 6.1.3 and 6.2.2.

Appendix 3. Prohibited Medications That May Impact SEL Treatment Efficacy or Decrease SEL Drug Level

Medication	Prohibited Period
Amiodarone	90 days prior to Enrollment through EOS
Bardoxolone	2 weeks prior to Enrollment through EOS
Ranolazine	2 weeks prior to Enrollment through EOS
Dronedarone	2 weeks prior to Enrollment through EOS
Dofetilide	2 weeks prior to Enrollment through EOS
Trimethoprim	2 weeks prior to Enrollment through EOS
Isavuconazole	2 weeks prior to Enrollment through EOS
Pyrimethamine	2 weeks prior to Enrollment through EOS
Cimetidine	2 weeks prior to Enrollment through EOS
Famotidine	2 weeks prior to Enrollment through EOS
Phenobarbital	2 weeks prior to Enrollment through EOT

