Phenytoin	2 weeks prior to Enrollment through EOT
Rifampin	2 weeks prior to Enrollment through EOT
St. John's wort	2 weeks prior to Enrollment through EOT

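### The prohibited-medication sensitivity analyses remove whole subjects even for drug use after the endpoint, and the cystatin C version removes them for drugs listed only for a creatinine effect

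*SAP*

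**What the plan says.** Three families of efficacy analysis carry the same sensitivity analysis.

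- **eGFRcr slope (SAP 6.1.3):** "excluding subjects who took prohibited medications that may affect SEL efficacy or decrease SEL drug level in the prohibited period". The drugs and periods are those of Appendix 3.
- **Kidney Clinical Events (SAP 6.2.2.2):** "Sensitivity analysis excluding subjects who took prohibited medications that may affect SEL efficacy or decrease SEL drug level in the prohibited period". It applies to both the proportion and the time-to-event analysis.
- **eGFRcys slope (SAP 6.2.2.3):** the same rule and the same list.

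SAP Appendix 3 names 14 drugs. For nine of them the period is "2 weeks prior to Enrollment through EOS". Amiodarone also runs to EOS but starts 90 days before Enrollment. For the four CYP3A4 inducers (phenobarbital, phenytoin, rifampin, St. John's wort) it is "2 weeks prior to Enrollment through EOT".

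Protocol 5.4 gives the reasons. On creatinine secretion it says: "Inhibitors of kidney transporter-mediated creatinine secretion may impact the assessment of efficacy". In Table 5-1, footnote b reads "May increase serum creatinine and decrease eGFR", and footnote g, attached to the inducers, reads "May result in a decrease in the concentration of SEL".

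**The concern.** A sensitivity analysis of this kind should show whether readings distorted by a prohibited drug drive the result. As written, it changes the population as well, and inclusion depends on what happens after randomization and, in part, after the outcome is already fixed. A subject whose 40% decline is dated at Week 24 is removed, event included, for a drug first taken at Week 70. If the result differed from the main analysis, nobody could say whether contaminated readings or the selection of subjects was responsible.

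Event counts also matter in their own right. SAP 6.2.2.2 reports a hazard ratio only for outcomes with more than 10 events and at least one in each arm, so deleting events could suppress a component result.

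For cystatin C, the stated reason for most of the list does not apply to the marker being analysed, so usable data are discarded.

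**Working it through.** **1. The plan's own figure.** SAP 1.3 gives a difference of 3.7, SD 10 (mL/min/1.73 m²/year) and one-sided alpha 0.15. Power ≈ Φ(3.7 / (10·√(2/n)) − 1.036).

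- n = 150 per arm: Φ(3.204 − 1.036) = 98.5% (stated 99%).
- n = 127 per arm: Φ(2.948 − 1.036) = 97.2% (stated 97%).

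Both reproduce. If the exclusion removed 30% of subjects, power would be 95.0% from 150 per arm (n = 105) and 92.2% from 127 per arm (n = 88). Lost power is not the problem.

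**2. Unit and period.** All three rules exclude subjects. Elsewhere in the 6.1.3 list the SAP excludes values instead (off-treatment SEL readings; readings after dialysis or transplant), so the distinction is deliberate. Counting Appendix 3 gives 10 drugs to EOS + 4 to EOT = 14. Neither period refers to the event date or to Week 84.

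**3. Kidney Clinical Events.**

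- SAP 6.2.1 dates an eGFR event at the index measurement. Later drug use cannot have affected that reading.
- Protocol 3.4 lists kidney failure as a reason to stop study drug, but not a 40% decline. Subjects with a 40% decline can stay on drug and on study.
- Protocol 5.4 and 6.4.2 record medications to the 30-day safety follow-up, or until remote follow-up begins.
- Protocol 6.5 moves subjects with kidney failure to remote follow-up after the 30-day EOT visit, and recording then stops.

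Post-event use is therefore captured mainly after 40%-decline events. The two event types have different chances of being deleted, and longer follow-up gives more chances for anyone.

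**4. Slopes.** The outcome stops at Week 84 (SAP 6.1.1, 6.2.1), while SAP Table 3-2 has visit windows to Week 168. First use after Week 84 removes every reading before it. The EOT limit for inducers can also fall after Week 84 or after a 40% decline.

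**5. Cystatin C.** Footnote b covers ranolazine, amiodarone, dronedarone, dofetilide, trimethoprim, isavuconazole, pyrimethamine, cimetidine and famotidine: 9 of 14. The eGFRcys equation in SAP 6.2.1 uses cystatin C, age and sex, with no creatinine term. The drugs left are 14 − 9 = 5: bardoxolone and the four inducers.

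**6. What cannot be computed.** The documents give no rate of prohibited-drug use and no event risk for this trial. Purely as an illustration, assume 15% event risk by Week 48, follow-up spread evenly over 48 to 144 weeks, yearly use of 5–20%, and use after the event at 1 to 3 times the earlier rate. A simulation then has 14–34% of excluded subjects removed only for post-event use, taking out 5–39% of all events. For the slope, 16–19% of those excluded go only for use after Week 84. The simulation treats medication as recorded after every event, so it overstates the kidney-failure part. A range this wide reflects its assumptions and is not an estimate.

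**The case against.** The stakes are limited. The primary estimand (SAP 6.1.3) uses all observed values whatever the concomitant medication. This is one of 11 sensitivity analyses listed for the eGFRcr slope, and no decision rule rests on it. Removing protocol deviators as subjects is a familiar per-protocol device, and the SAP has a Per-Protocol set. All of that stands, and it bounds the importance of the point.

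Whole-subject removal is also sometimes right. The prohibited period covers Visits A, B, C and 1, whose averages form the baselines. Because the slope outcome is change from baseline, a contaminated baseline affects every change value. That stands too, and the fix keeps subject-level exclusion there. The confirmation rule, with a second reading at least 4 weeks later, already limits the effect of short courses on kidney events.

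A reader might infer that the rule biases the comparison for or against SEL. The documents do not show this. Treatment is double-blind, no effect of SEL on use of these drugs is documented, and exclusion on use does not by itself favour an arm. A reader might also size the loss from Phase 2 urinary tract infections (Table 1-4: 12 + 5 = 17 of 333, 5.1%). An infection is not a course of trimethoprim, which is prohibited here, and the rates at the trial dose were alike (6.0% on 18 mg, 5.9% on placebo). Nor do the documents say that subjects with events take more of these drugs.

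None of this justifies letting use after the endpoint decide inclusion, or applying the creatinine list to cystatin C.

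**Conclusion.** The point holds as a defect in three sensitivity analyses. Whole subjects are excluded for use up to EOS (10 drugs) or EOT (4 drugs), with no limit at the endpoint. Kidney events, mainly 40% declines, can be deleted for use after they were dated, and slope data through Week 84 for use after that week. The eGFRcys version applies 9 of 14 drugs on a rationale that concerns creatinine only.

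The stronger inferences, that the primary result is compromised or that power is materially lost, are not supported. The size and direction of the selection effect are unknown. The conclusion rests on reading the exclusion wording literally and on medications being recorded after the endpoint as Protocol 5.4 specifies.

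**What to change.** 1. **Exposure window.** For Kidney Clinical Events, count only use before the index event date, or before censoring for subjects without an event. For slopes, count only use up to the last analysed visit (Week 84).
2. **eGFRcys list.** Restrict it to bardoxolone and the four CYP3A4 inducers.
3. **Value-level version for eGFRcr.** Drop eGFRcr readings taken during use of a creatinine-affecting drug plus a stated washout, identically in both arms. Applied to event confirmation, this also covers a drug taken between the index and confirming readings. Keep dialysis, transplant and renal death as events. Retain subject-level exclusion where use overlaps the Visit A/B or Visit C/1 baseline readings.
4. **Inducers.** Apply any rule equally in both arms. Dropping readings only where SEL exposure may be lowered would act on the SEL arm alone.

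The cost is SAP wording and programming from medication dates that are already collected. The downside is that a washout length must be chosen and a rule set for partial medication dates, which SAP 7.4.2 anticipates.
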